7.3. Visit 3: Out-patient Follow-up (24 hours/Day 1)

- Obtain vital signs
- Review and update concomitant medications
- Perform symptom directed PE
- Obtain blood samples for the following:
 - PK measurement at 24 hours (+/- 2 hours)
- Counsel women of child-bearing potential on the avoidance of pregnancy
- Counsel the subject not to receive any botulinum toxin preparation (e.g., Botox) for 4 months after injection.
- Assessment of AEs and SAEs

7.4. Visit 4: Out-patient follow-up Visit (48 hours/Day 2)

- Obtain vital signs
- Review and update concomitant medications
- Perform symptom directed PE
- Obtain blood samples for the following:
- PK measurement at 48 hours (+/- 2 hours) Counsel women of child-bearing potential on the avoidance of pregnancy
- Counsel the subject not to receive any botulinum toxin preparation (e.g., Botox) for 4 months after injection
- Assessment of AEs and SAEs

7.5. Visit 5: Out-patient Follow-up (72 hours) Cohorts 1-3

- Obtain vital signs
- Review and update concomitant medications
- Perform symptom directed PE
- Obtain blood samples for the following:
 - PK measurement at 72 hours (+/- 2 hours)
- Counsel women of child-bearing potential on the avoidance of pregnancy
- Counsel the subject not to receive any botulinum toxin preparation (e.g., Botox) for 4 months after injection.
- Assessment of AEs and SAEs

7.6. Visit 6: Out-patient Follow-up (Day 4)

- Obtain vital signs
- Review and update concomitant medications
- Perform symptom directed PE
- Obtain blood samples for the following:
 - PK measurement
 - MNA
- Obtain urine sample urine HCG for women of child bearing potential
- Counsel women of child-bearing potential on the avoidance of pregnancy
- Counsel the subject not to receive any botulinum toxin preparation (e.g., Botox) for 4 months after injection.
- Assessment of AEs and SAEs

7.7. Visit 7: Out-patient Follow-up (Day 8± 1)

- Obtain vital signs
- Review and update concomitant medications
- Perform symptom directed PE
- Obtain blood samples for the following:
 - Clinical Safety Labs
 - PK measurement
 - Serum sample to store for future use (if subject gave consent)
- Counsel women of child-bearing potential on the avoidance of pregnancy

- Counsel the subject not to receive any botulinum toxin preparation (e.g. Botox) for 4 months after injection
- Assessment of AEs and SAEs

7.8. Visit 8: Out-patient Follow-up (Day 15± 1)

- Obtain vital signs
- Review and update concomitant medications
- Perform symptom directed PE
- Obtain blood samples for the following:
 - Clinical Safety Labs
 - PK measurement
 - ADA (Cohorts 1-3 only)
- Assessment of AEs and SAEs
- Counsel women of child-bearing potential on the avoidance of pregnancy
- Counsel the subject not to receive any botulinum toxin preparation (e.g. Botox) for 4 months after injection
- Assessment of COVID-19 vaccination status

7.9. Visit 9: Out-patient Follow-up (Day 30 ± 1)

- Obtain vital signs
- Review and update concomitant medications
- Perform symptom directed PE
- Obtain blood samples for the following:
 - Clinical Safety Labs
 - PK measurement
 - MNA
 - ADA (Cohorts 1-3 only)
 - Serum sample to store for future use (if subject gave consent)
- Assessment of AEs and SAEs
- Counsel women of child-bearing potential on the avoidance of pregnancy
- Counsel the subject not to receive any botulinum toxin preparation (e.g. Botox) for 4 months after injection

- Assessment of COVID-19 vaccination status.

7.10. Visit 10: Out-patient Follow-up (Day 45± 3)

- Obtain vital signs
- Review and update concomitant medications
- Perform symptom directed PE
- Obtain blood samples for the following:
 - PK measurement
 - ADA
 - MNA (Cohort 4 only)
- Perform urine pregnancy test on women of child-bearing potential
- Assessment of AEs and SAEs
- Counsel women of child-bearing potential on the avoidance of pregnancy
- Counsel the subject not to receive any botulinum toxin preparation (e.g. Botox) for 4 months after injection
- Assessment of COVID-19 vaccination status.

7.11. Visit 11: Out-patient Follow-up (Day 60 ± 3)

- Obtain vital signs
- Review and update concomitant medications
- Perform symptom directed PE
- Obtain blood samples for the following:
 - PK measurement
 - MNA
 - ADA
- Assessment of AEs and SAEs
- Counsel women of child-bearing potential on the avoidance of pregnancy
- Counsel the subject not to receive any botulinum toxin preparation (e.g. Botox) for 4 months after injection
- Assessment of COVID-19 vaccination status.

7.12. Visit 12: Out-patient Follow-up (Day 90±3)

- Obtain vital signs
- Review and update concomitant medications
- Perform symptom directed PE
- Obtain blood samples for the following:
 - PK measurement
 - MNA
 - ADA
- Assessment of AEs and SAEs
- Counsel women of child-bearing potential on the avoidance of pregnancy
- Counsel the subject not to receive any botulinum toxin preparation (e.g. Botox) for 4 months after injection
- Assessment of COVID-19 vaccination status.

7.13. Visit 13: Final Visit / Early Termination Visit for Cohorts 1-3 (Day 120±3) / Cohort 4 (Day 120±3)

- Obtain vital signs
- Review and update concomitant medications
- Perform symptom directed PE
- Obtain blood samples for the following:
 - Clinical Safety labs (Cohorts 1-3 Only)
 - PK measurement
 - MNA
 - ADA
- Obtain urine sample for dipstick analysis
- Perform urine pregnancy test on women of child-bearing potential
- Assessment of AEs and SAEs
- Counsel women of child-bearing potential on the avoidance of pregnancy
- Counsel the subject not to receive any botulinum toxin preparation (e.g. Botox) for 4 months after injection
- Assessment of COVID-19 vaccination status.

**7.14. Visit 14: Final Visit/ Early Termination for Subjects in Cohort 4
(Day 180±3)**

- Obtain vital signs
- Review and update concomitant medications
- Perform symptom directed PE
- Obtain blood samples for the following:
 - Clinical Safety Labs
 - PK measurement
 - ADA
- Obtain urine sample for dipstick analysis
- Perform urine pregnancy test on women of child-bearing potential
- Assessment of AEs and SAEs
- Counsel women of child-bearing potential on the avoidance of pregnancy
- Counsel the subject not to receive any botulinum toxin preparation (e.g. Botox) for 4 months after injection
- Assessment of COVID-19 vaccination status.

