3.2.2. Secondary Endpoints

- The pharmacokinetic assessment of C_{max} , T_{max} and $AUC_{(0-t)}$ as measured by the validated Battelle Mouse Neutralization Assay (MNA) for serotypes A and B
 - Pharmacokinetic samples will be tested by MNA at pre-dose and on Days 4, 30, 60, 90, and 120 for Cohorts 1-3.
 - Pharmacokinetic samples will be tested by MNA at pre-dose, 2-hours post-dose (future use), and on Days 4, 30, 45, 60, 90, and 120 for Cohort 4.
- The assessment of C_{max} , T_{max} , half-life (α and β), MRT, and $AUC_{(0-t)}$ for each of the monoclonal antibodies of G03-52-01 as measured by a validated electrochemiluminescence assay (ECLA) or validated enzyme-linked immunosorbent assay (ELISA).
 - Pharmacokinetic samples will be tested by ECLA or ELISA at pre-dose, 2, 4, 8, 24, 48, and 72 hours post injection, and on Days 4, 8, 15, 30, 45, 60, 90, and 120 for Cohorts 1-3.
 - Pharmacokinetic samples will be tested by ECLA or ELISA at pre-dose, 6 hours post-dose, and on Days 1, 2, 4, 8, 15, 30, 45, 60, 90, 120, and 180 for Cohort 4.
- Samples will be tested to evaluate presence of anti-drug antibodies (ADA) collected for all cohorts.
 - Samples will be tested for ADA at pre-dose, 15, 30, 45, 60, 90, and 120 for Cohorts 1-3.
 - Samples will be tested for ADA at pre-dose and on Days 45, 60, 90, 120, and 180 for Cohort 4.

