4.2.4 Handling of Withdrawals

Subjects who are withdrawn prior to dosing may be replaced. Following dosing, one subject per cohort may withdraw prior to the completion of Visit 11 (Day 60) or was noncompliant with all PK draws through Visit 6 (Day 4) without being replaced. Should more than one subject from the same cohort voluntarily withdraw from the study who did not meet the above criteria, those subjects may be replaced. Subjects who withdraw or are withdrawn from the study who received any amount of the study product will be encouraged to continue follow-up (with subjects' consent) for safety. Subjects withdrawing will be asked to complete a final termination visit if they do not wish to be followed per protocol.

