15. The Hypersensitivity Panel includes cytokine and complement panels, IgE, and tryptase. Draw 14ml prior to dosing. If a subject develops anaphylaxis or anaphylactoid reaction, an additional 14 mL sample will be drawn during the event and another will be drawn after the event.
16. MNA: To be drawn pre-dose for All Cohorts. Cohort 4 subjects will also have a 2-hour post dose optional (+/- 10 minutes) draw.
18. Cohorts 1-3 only.

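### The schedule tables and section 7.14 assign Cohort 4 early termination to different visits, and under the tables a 100 mg cohort subject who leaves early has no exit safety labs, dipstick or pregnancy test

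*Protocol*

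**What the plan says.** Four places in the current text describe what happens when a Cohort 4 subject leaves early.

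- **Protocol 4.2.4.** Dosed subjects who withdraw are encouraged to stay in follow-up. Otherwise, "Subjects withdrawing will be asked to complete a final termination visit if they do not wish to be followed per protocol". The section does not say which numbered visit this is for Cohort 4.
- **Protocol Appendix A and SAP Table 3-2.** The early-termination label sits on the Visit 13 column without a cohort limit. The Visit 14 column is marked as Cohort 4 only and has no early-termination label. In the Visit 13 column, safety labs, urine pregnancy test and dipstick carry footnote 18: "18. Cohorts 1-3 only". The SAP repeats the footnote.
- **Protocol 7.13.** The heading is "Visit 13: Final Visit / Early Termination Visit for Cohorts 1-3 (Day 120±3) / Cohort 4 (Day 120±3". The list below it includes "Clinical Safety labs (Cohorts 1-3 Only", then, with no cohort limit, "Obtain urine sample for dipstick analysis" and "Perform urine pregnancy test on women of child-bearing potential". It also includes MNA.
- **Protocol 7.14.** The heading is "Visit 14: Final Visit/ Early Termination for Subjects in Cohort 4". The list has safety labs, PK, ADA, dipstick and pregnancy test, but no MNA.

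Section 6.5.2 places the safety laboratory tests at screening and end of study. Section 3.2.1, repeated in SAP 2.2.1, makes change from baseline in safety laboratory values up to the final follow-up visit a primary endpoint.

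**The concern.** Site staff usually work from the schedule of events, and here it disagrees with the visit text. A coordinator using Appendix A would send a departing Cohort 4 subject to the Visit 13 column and, because of footnote 18, take no safety labs, dipstick or pregnancy test. A coordinator using 7.14 would do all three. Nothing in either document says which source prevails.

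What is at stake is the last safety laboratory value of a subject who leaves the highest-dose cohort of a first-in-human study. In Cohorts 1-3 the same column does collect labs at early termination, so under the tables the omission would fall on the 100 mg cohort alone.

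A second, smaller conflict affects every Cohort 4 subject at Day 120, whether or not anyone withdraws. Section 7.13 lists dipstick and pregnancy test for all cohorts, while footnote 18 limits both to Cohorts 1-3.

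**Working it through.** No stated power or sample-size figure is involved. The check is an item-by-item comparison, with the blood volumes in protocol Table 2 as a cross-check.

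**Step 1. What a Cohort 4 early leaver would have done at the termination visit**

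| Source | Safety labs | Dipstick | Urine pregnancy test | MNA |
|---|---|---|---|---|
| Appendix A / SAP Table 3-2, Visit 13 and early-termination column | No (footnote 18) | No (footnote 18) | No (footnote 18) | Yes, per Table 2 at Visit 13 |
| 7.13, if its heading is read as covering Cohort 4 | No | Yes | Yes | Yes |
| 7.14 | Yes | Yes | Yes | No |

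The MNA row of Appendix A is misaligned in the text available, so the MNA entries rest on 3.2.2, 7.13, 7.14 and Table 2.

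**Step 2. Is the lab restriction real?** Table 2 gives 9 mL for safety labs, 6 mL for PK, 30 mL for MNA and 6 mL for ADA.

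- Visit 13, Cohorts 1-3: 9 + 6 + 30 + 6 = 51 mL. Stated: 51.
- Visit 13, Cohort 4: 6 + 30 + 6 = 42 mL. Stated: 42. With labs it would be 51.
- Visit 14, Cohort 4: 9 + 6 + 6 = 21 mL. Stated: 27. With MNA it would be 51.

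The Visit 13 figures reproduce exactly, and the Cohort 4 total has no room for safety labs. The restriction is therefore deliberate. The Visit 14 total is 27 - 21 = 6 mL too high. That error carries into the Cohort 4 grand total (417 stated, against 4 + 9 + 45 + 78 + 210 + 36 + 15 + 14 = 411 from the rows), but it does not bear on this point. Neither 21 nor 27 allows for a 30 mL MNA draw.

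**Step 3. Size of the gap.** Table 2 schedules Cohort 4 safety labs on Days 0, 8, 15, 30 and 180. For a subject leaving on Day D, after Day 30 and before the Day 180 visit, the tables leave this time without labs:

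gap = D - 30

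- D = 60: 60 - 30 = 30 days
- D = 90: 90 - 30 = 60 days
- D = 120: 120 - 30 = 90 days

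**Step 4. How many subjects.** Cohort 4 has 10 planned subjects (8 active, 2 placebo). Only those who withdraw, decline continued follow-up and attend a termination visit are exposed. Neither document gives a dropout rate, so no expected number can be stated.

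**The case against.** The best defence is that the visit text agrees with itself. The 7.13 heading can be read as early termination for Cohorts 1-3 and an ordinary Day 120 visit for Cohort 4, with 7.14 then supplying the Cohort 4 early-termination visit. On that reading, footnote 18 simply moves Cohort 4's final tests from Day 120 to Day 180, as the end-of-study pregnancy test in section 7.5.1.3 does. Section 6.5.2 also points towards labs at exit. Vital signs, symptom-directed examination and AE review occur under both 7.13 and 7.14, AEs are followed to resolution or stability (8.4), and the analyses are descriptive.

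All of this is fair, and it means 7.13 should not be counted as a firm second definition. It does not remove the conflict between 7.14 and the two schedule tables. Section 6.5.2 does not say that early termination counts as end of study, and the minimum list for an unscheduled visit (7.15) contains no labs.

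A reader might infer several stronger points that the documents do not support:

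- **A 150-day lab gap.** The interval 180 - 30 = 150 days is the schedule for every Cohort 4 completer and is not caused by this conflict. Misuse of the Visit 13 column is plausible mainly up to about Day 120.
- **Loss of MNA data.** Leaving MNA out of 7.14 matches the planned schedule, which tests MNA "on Days 4, 30, 45, 60, 90, and 120 for Cohort 4" and not later. Earlier MNA samples would still exist. The documents are only silent on a subject who leaves before Day 120.
- **Early-termination results tabulated as Day 120.** The SAP summarises by nominal time point and does not say how termination visits are mapped. This is speculative, and it would apply equally to Cohorts 1-3.
- **Every withdrawal affected.** Section 4.2.4 only asks for a termination visit from those who decline further follow-up.

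**Conclusion.** The concern holds as an inconsistency in the current documents with a consequence for data collection. Appendix A and SAP Table 3-2 give a Cohort 4 early leaver no exit safety labs, dipstick or pregnancy test, while section 7.14 gives all three. For safety labs, the tables' version also sits badly with 6.5.2 and with a primary endpoint that runs to the final follow-up visit.

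The effect is limited. At most the 10 planned subjects are exposed, not counting any replacements, and only if someone leaves early on these terms. The unobserved period is D - 30 days for a leaver after Day 30, about 90 days near Day 120. Labs from Days 0, 8, 15 and 30 would remain for such a subject. This assumes that the site follows the schedule tables rather than 7.14 and orders no unscheduled labs. The point should be corrected, but it does not threaten the study's main conclusions.

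**What to change.** Reconcile 7.13, 7.14, Appendix A with footnote 18, and SAP Table 3-2 so that one early-termination visit and one assessment list apply to Cohort 4. That list should be consistent with the end-of-study safety labs that 6.5.2 and the primary endpoint already call for. In the same edit:

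- Make the 7.13 heading unambiguous about whether its early-termination label covers Cohort 4.
- Settle whether dipstick and urine pregnancy test are done in Cohort 4 at Day 120, since 7.13 and footnote 18 disagree.
- State whether MNA is drawn at the termination visit for a Cohort 4 subject leaving before Day 120.
- Name in 4.2.4 the visit that serves as the final termination visit for each cohort.

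The cost is a wording change in two documents and about one 9 mL lab draw per Cohort 4 early leaver, plus one 30 mL MNA draw if the sponsor decides to include it.

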7.15. Unscheduled Visit

A subject may return to the clinic for an unscheduled visit at any time. The following activities at a minimum should be performed:

- Obtain vital signs
- Perform symptom directed PE as appropriate
- Review and update concomitant medications
- Assessment of AEs and SAEs
- Assessment of COVID-19 vaccination status.

8. ASSESSMENT OF SAFETY

Regulatory requirements including the FDA regulations and ICH Guidelines for GCP set forth safety monitoring and reporting responsibilities of sponsors and investigators to ensure the safety and protection of human subjects participating in clinical trials.

Responsibilities

Investigators participating in this clinical trial are responsible for and will:

- evaluate subject safety including assessment of AEs for seriousness, severity, and causality;
- notify the sponsor (Ology Bioservices) of SAEs immediately;
- provide detailed written reports, including necessary documentation requested by the sponsor or IRB/Independent Ethics Committee (IEC), promptly following immediate initial reports, and;
- Inform the IRB/IEC of AEs as required by applicable regulatory requirements.

8.1. Specification of Safety Parameters

Definitions

Adverse events

ICH E6(R2) defines an AE as any untoward medical occurrence in a patient or clinical investigation subject administered a pharmaceutical product and which does not necessarily have a causal relationship with this treatment. An AE can therefore be any unfavorable and unintended sign (including an abnormal laboratory finding), symptom, or disease temporally associated with the use of medicinal (investigational) product, whether or not related to the medicinal (investigational) product.

FDA defines an AE as any untoward medical occurrence associated with the use of a drug in humans, whether or not considered drug related.

Serious Adverse Events

An SAE is any untoward medical occurrence that at any dose:

- Results in death,
- Is life-threatening*,
- Requires inpatient hospitalization or prolongation of existing hospitalization,
- Congenital anomaly/birth defect;
- Persistent or significant incapacity or substantial disruption of the ability to conduct normal life functions

**Life-threatening adverse event. An adverse event is considered “life-threatening” if, in the view of either the investigator or sponsor, its occurrence places the patient or*

subject at immediate risk of death. It does not include an adverse event, had it occurred in a more severe form, might have caused death.

Unexpected

An adverse reaction, the nature or severity of which is not consistent with the applicable product information (e.g. Investigator's Brochure for an unapproved investigational product or package insert/summary of product characteristics for an approved product).

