Doses will escalate to 25 mg and then to 50 mg up to 100mg provided there are no safety concerns. The nonclinical IND-enabling toxicology studies were designed to support this clinical design with intramuscular route of administration. Based on data received from the Day 60 blinded interim safety and PK analysis, it was determined to escalate to 100mg single dose.

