Since this is a first-in-human study, administration of the study products to subjects in a cohort will occur over a period of up to two weeks to allow careful observation of individuals for adverse events. Two sentinel subjects within each cohort will be admitted initially and will be administered a single IM injection, and the randomization scheme will be designed to ensure that one subject will receive G03-52-01 and the other will receive placebo. The dosing of the remaining eight subjects within that cohort will not be initiated until at least 24 hours have passed and no adverse events have occurred that meet halting criteria, and no safety signals have occurred that in the opinion of the investigator warrant further investigation. The remaining eight subjects in the cohort will be admitted as scheduled without delay. An alternate subject will be admitted to the unit for each two-subject group. Up to four alternates per cohort will be recruited. Dose escalation will not occur until safety data through Day 8 is reviewed by the Safety Review Committee (SRC) composed of the Principal Investigator (PI), Ology Bioservices Medical Monitor, and the ICON Medical Monitor.

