8.3.2. Serious Adverse Events

The following procedures will apply to all serious adverse events:

- The Principal Investigator will report any SAE to ICON PVSS within 24 hours of awareness.
- ICON PVSS will perform an initial check of the SAE for missing elements and then inform the ICON MM, and the ISM.
- ICON PVSS will record the information on the appropriate serious adverse event report form and send to DOD PVG and to Ology Bioservices
- Each SAE will be reviewed and followed to resolution or stability by a study physician
- SAEs will be collected on each subject until his/her last study visit.

Any AE that meets a protocol-defined serious criterion must be submitted immediately (within 24 hours of site awareness) on an SAE form to Ology Bioservices at the following address:

ICON PVSS

ICON plc PVSS

**[name]
[name]
SAE Email Address: [contact]**

ICON Medical Monitor:

[name]

ICON Early Phase Services

[name]
[name], USA
SAE [contact]
SAE Email Address: [contact]

ICON PVSS will send AE/SAE information to Ology Bioservices, Inc.

Ology Bioservices	Ology Bioservices, Inc.
	[name]
	[name], USA
	SAE [contact]
	SAE [contact]
	SAE Email Address: [contact]

Other supporting documentation of the event may be requested by Ology Bioservices and should be provided as soon as possible.

ICON plc PVSS will send SAEs with the ICON Drug Safety Physician assessment of causality, expectedness, and any impact on the benefit-risk ratio of the IMP to Ology Bioservices and DOD PVG. The ICON medical monitor and clinical project manager will be notified of the SAE by DOD PVG. The ICON medical monitor will review and assess the SAE for potential impact on study subject safety and protocol conduct.

At any time after completion of the study, if the investigator becomes aware of an SAE that is suspected to be related to study product, the investigator will report the event to ICON PVSS.

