8.5. Halting Rules

8.5.1. Halting Criteria for the Study

Study dosing can be halted at any time if medically indicated. Study dosing must be stopped, and a review of available safety data will be conducted by the SRC if any of the following occur:

1. Death of a dosed subject following injection and prior to the subject's last visit that was not the result of trauma or accident, and possibly related to study product.
2. Occurrence of a life-threatening allergic/hypersensitivity reaction (anaphylaxis) in any subject, manifested by bronchospasm with or without urticaria or angioedema or requiring hemodynamic support with pressor medications or mechanical ventilation.
3. One subject with an SAE.
4. Two or more subjects with a Grade 3 AE in the same organ class (systemic toxicity, clinical laboratory tests or vital signs) regardless of relatedness to study drug. An exception to this includes scenarios where there are obvious and acceptable physiological explanations for a Grade 3 abnormality (e.g., Grade 3 hematuria in a menstruating female).

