10.2. Planned Interim Analyses

A blinded interim safety and PK analysis is planned for this study to analyze all PK, ADA, and MNA samples for Cohorts 1-3 through Day 60 and Day 120. A second blinded interim safety analysis is planned to analyze all PK, ADA, and MNA samples for Cohort 4 through Day 90. Stopping criteria are for safety and are defined in section 9.5.

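### The SAE definition has no important-medical-event criterion, so a lone Grade 3 allergic reaction can be recorded as non-serious and, if it is the study's first Grade 3 AE in its organ class, force no dosing stop

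*Protocol*

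**What the plan says.** **Definition.** Protocol 8.1 lists five SAE criteria: death; life-threatening; "Requires inpatient hospitalization or prolongation of existing hospitalization"; congenital anomaly; and incapacity or substantial disruption of normal life. SAP 3.15 repeats the five and adds none. The life-threatening criterion is met if either the investigator or the sponsor sees an immediate risk of death. Its footnote leaves out events that could have been fatal only in a more severe form.

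**Reporting.** Under Protocol 8.3.2, "Any AE that meets a protocol-defined serious criterion must be submitted immediately", with a 24-hour limit. The same section has the independent safety monitor (ISM) informed of each SAE. For other AEs, 8.6.1 leaves ISM review to need.

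**Grading.** Appendix B (Systemic Reactions) makes an allergic reaction Grade 3 if there is generalized urticaria, angioedema or anaphylaxis, or if epinephrine is needed.

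**Mandatory stops (8.5.1).**
- Rule 1: a possibly related death.
- Rule 2: "Occurrence of a life-threatening allergic/hypersensitivity reaction (anaphylaxis) in any subject, manifested by bronchospasm with or without urticaria or angioedema", or one that needs pressors or mechanical ventilation.
- Rule 3: "One subject with an SAE".
- Rule 4: "Two or more subjects with a Grade 3 AE in the same organ class (systemic toxicity, clinical laboratory tests or vital signs"), whatever the relatedness.

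Dosing may also be halted at any time on medical grounds.

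**Escalation.** 8.5.2 has two criteria: more than 25% of a cohort with Grade 2 or higher AEs in one organ class, and a specific AE that rises in severity from one cohort to the next in the same or a greater number of subjects. 8.5.3 requires the Safety Review Committee (SRC) to agree unanimously, before escalating, that there is no safety signal. 8.6.4 assigns the routine Day 8 review to Cohorts 1 to 3. A later sentence there is not tied to a cohort: if any study-halting or escalation-halting criterion is met, the SRC meets and advises on further dosing.

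**The concern.** Allergic reaction is the hazard that Protocol 2.3.1 singles out, with angioedema and bronchospasm among the named signs, and 6.5.3 takes a pre-dose hypersensitivity sample from every subject. Yet a Grade 3 allergic reaction is not serious by virtue of its grade. If it is treated early and resolves in the unit, the five-item list may not capture it.

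Two things are then at stake. The first is classification: SAE counts, rapid reporting and ISM notice all follow from it, and 8.3.3 reserves expedited FDA reporting for events that are serious as well as unexpected. The second is stopping: one SAE stops dosing, whereas one non-serious Grade 3 AE does not.

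Under the current version the stopping question concerns Cohort 4. Protocol 2.2 says: "Based on data received from the Day 60 blinded interim safety and PK analysis, it was determined to escalate to 100mg single dose". Section 10.2 shows that this interim covered "MNA samples for Cohorts 1-3 through Day 60 and Day 120", so those cohorts had already been dosed. A stop can still protect people in Cohort 4, because Section 4 says that dosing within a cohort "will occur over a period of up to two weeks to allow careful observation of individuals for adverse events", and after the 24-hour sentinel hold the other eight subjects follow on schedule.

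**Working it through.** **Step 1. Trace one case through the text.** Take one Grade 3 allergic reaction in Cohort 4, without bronchospasm, pressors or ventilation.

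| Provision | What it needs | This case |
|---|---|---|
| SAE: death, congenital anomaly | the outcome itself | not met |
| SAE: life-threatening | immediate risk of death, in the investigator's or sponsor's view | not met, by assumption |
| SAE: hospitalization | admission or a longer stay | need not be met; the planned stay is up to 12 hours with discharge from about 8, so an early reaction can resolve inside it |
| SAE: incapacity | persistent or significant incapacity, or substantial disruption | need not be met; 8.2.1 calls severe events usually incapacitating and defers to Appendix B, which grades allergy by type or treatment |
| Rule 1 | a death | not met |
| Rule 2 | life-threatening, with bronchospasm, pressors or ventilation | not met |
| Rule 3 | one SAE | not met, since no SAE criterion is |
| Rule 4 | two subjects, Grade 3, same organ class | not met, unless an earlier subject in any cohort already had one |
| 8.5.2, first criterion | more than 25% of the cohort | 1/10 = 10%, not met by this case alone |
| 8.5.2, second criterion | same AE at lower severity in the previous cohort, in no more subjects | met only if one Cohort 3 subject had it at a lower grade; then 8.6.4 requires an SRC meeting, not a stop |

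**Step 2. Where the event is lost and where it stays.**
- Lost: the SAE primary endpoint, Table 14.3.2.2, the 24-hour report and the automatic ISM notice.
- Kept: the AE primary endpoint (Protocol 3.2.1), the AE tables including maximum severity (Table 14.3.1.3), probably the reactogenicity tables (14.3.1.5 to 14.3.1.7), and Listing 16.2.7.4 if the hypersensitivity panel is processed.
- The Cohort 4 active SAE count would read 0/8 instead of 1/8. No decision rule uses that proportion.

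**Step 3. How likely is such a case?** The plan's only detection figure is in Protocol 10.1: 0.728 to 0.996 at event rates of 0.15 and 0.5, worded for ten subjects. The formula is 1 − (1 − p)^n. With n = 10 it gives 0.803 and 0.999; with n = 8 it gives 0.7275 and 0.9961. The printed figure therefore belongs to eight active subjects. That wording is a separate matter and nothing here depends on it.

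The documents give no rate for the event in question, so the rates below are assumptions, with n = 8 active subjects:

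| Assumed rate per active subject | Chance of at least one case |
|---|---|
| 0.1% | 0.8% |
| 0.5% | 3.9% |
| 1% | 7.7% |
| 2% | 14.9% |
| 3% | 21.6% |
| 5% | 33.7% |

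At 1%: 1 − 0.99^8 = 1 − 0.9227 = 0.0773. Exactly one case: 8 × 0.01 × 0.99^7 = 0.0746. Two or more: 0.0773 − 0.0746 = 0.0027. At low rates nearly all the risk is therefore a single case, which rule 4 does not catch without an earlier Grade 3 AE in the class.

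**Step 4. How many would a stop spare?** Protocol Sections 4 and 4.2.1 refer to two-subject groups. The sentinel pair holds one active subject; the other four pairs hold seven (three pairs of two, one pair with one). Assume that a case is equally likely in any active subject and that a stop spares all later pairs.
- Case in the active sentinel: 7 spared.
- Case in one of the other seven: the numbers spared, summed over the seven, are (7² − (4 + 4 + 4 + 1))/2 = 18, wherever the placebo falls.
- Mean over all eight: (7 + 18)/8 = 3.1. Leaving out the sentinel, whose case the 24-hour hold can already address: 18/7 = 2.6.
- Dosing one at a time would give (7 + 6 + … + 0)/8 = 3.5.

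**The case against.** The case on the other side is substantial.

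1. **Rule 4 is study-wide.** It has no cohort limit, ignores relatedness and uses broad classes. Appendix B puts headache, fatigue and myalgia beside allergic reaction under systemic reactions. An earlier Grade 3 systemic AE, even on placebo, could make one Cohort 4 case the second. This stands. A reader might infer that Cohort 4 always needs two cases of its own; the text does not say so.
2. **Cohort 4 is not left wholly to judgement.** The second criterion of 8.5.2 with the general sentence in 8.6.4 can compel an SRC meeting. This stands, but it needs an earlier, milder case in Cohort 3 and yields a meeting, not a stop.
3. **No safety data disappear.** This stands. A reader might infer that the event drops out of the primary endpoints. It drops out of the SAE endpoint only.
4. **The higher rates have no support.** Protocol 2.1.2 gives about 1% anaphylaxis for the current equine antitoxin, 2.2 expects substantially less here, and 2.3.1 lists no allergic reaction among the related AEs of the two predecessor products. These are not bounds on this narrower event, but they do not support 5%.
5. **Investigators would act anyway.** They may halt on medical grounds, hold after the sentinels, or raise a safety concern that brings an SRC meeting. Each depends on someone's judgement. So would the added criterion, which therefore narrows the gap without closing it.
6. **General rules apply regardless.** Protocol Section 8 refers to FDA regulations and ICH guidelines in general terms. That adds no item to the list to which 8.3.2 ties SAE submission.

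**Conclusion.** The concern holds in a narrow form. Applied as written, the five-item list lets one Grade 3 allergic reaction of the kind described be recorded as non-serious. No mandatory stop then follows if it is the first Grade 3 AE in its organ class in the whole study. In Cohort 4 the other safeguards are discretionary, apart from the conditional SRC meeting.

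The size is modest: 7.7% for at least one such case at an assumed 1% rate, and about 2.6 to 3.1 active subjects spared on average by a stop with two-subject groups. Both figures rest on assumptions that the documents neither confirm nor exclude. The documents do not support a claim that Grade 3 allergic reactions in general escape the stopping rules: those that are life-threatening, lengthen the stay or incapacitate are SAEs, and a second Grade 3 AE in the class stops dosing.

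No statistical method is affected. This is a cheap improvement to a definition that feeds a primary endpoint and a halting rule in a first-in-human trial.

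**What to change.** Add a sixth criterion to Protocol 8.1 and SAP 3.15, for example: *an important medical event that, in the judgement of the investigator or the sponsor, jeopardises the subject or needs intervention to prevent an outcome listed above, such as an epinephrine-treated allergic reaction, angioedema or allergic bronchospasm.* The examples give the judgement a fixed reference. Bronchospasm is named because rule 2 reaches it only within a life-threatening reaction. State in 8.5.1 that rule 3 applies to these events. If the sponsor wants a stop that does not depend on judgement, a one-subject rule for Grade 3 allergic reactions in 8.5.1 would be more direct.

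If Cohort 4 dosing is complete, the stopping benefit has gone. In that case, carry out a blinded medical review of all Grade 3 allergic reactions before database lock and list them in SAP Section 14.3.2, whose title already extends beyond serious events.

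Cost: one line in each document, one sentence in 8.5.1, a CRF check-box and at most one listing. The downside is a few more expedited reports and possibly one extra SRC pause. Generalized urticaria without epinephrine would still rest on judgement.
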